#### 9.1.1.1. During Follow-up

All ongoing AEs with onset in the treatment period will have to be followed up after the hospital discharge visit until the outcome of the event is ‘recovering’ (for chronic conditions), or recovered (/with sequelae), or until end of study and until all queries related to these AEs have been resolved.

All SAEs, including fatal events, related to IMP with onset during the follow-up period (from the hospital discharge visit until end of study) will have to be collected and followed until resolved.

### 9.1.2. After End of Study

After the end of study, new SAEs related to IMP must be reported to the sponsor via the regular SAE reporting system.

## 9.2. Serious Adverse Event Reporting and Timelines

### 9.2.1. Initial Reporting of Serious Adverse Events

SAEs that should be reported within 24 hours on the SAE form are:

- Events with fatal outcome
- New life-threatening events, defined as:
  - Cardiac event requiring CPR or medical resuscitation (adrenaline use etc.) – can be caused by severe arrhythmia or other
  - Life-threatening spontaneous bleeding requiring blood transfusion and / or surgical intervention
  - Thrombo-embolic event with life-threatening hemodynamic or pulmonary instability
  - New life-threatening organ failure / dysfunction
  - Liver: AST, ALT > 20 x upper limit of normal (ULN) OR Bilirubin > 10 x ULN
  - Kidney: Creatinine > 6 x ULN – or newly developed anuria  $\leq$  100 mL urine production over 24h
  - Cardiovascular:
    - Norepinephrine > 1  $\mu$ g/kg/min or equivalent
    - Troponin I: levels consistent with myocardial infarction as defined by manufacturer
  - Coagulation: Thrombocyte count < 20.000 /  $\mu$ L or partial thromboplastin time (PTT) > 2.5 x ULN
  - Life-threatening infections other than COVID-19 which require immediate antibiotic treatment and/or additional medical / surgical intervention
  - Life-threatening infusion reactions which require immediate intensification of existing intensive care treatment, including but not limited to additional vasopressor or fluid support, or high dose corticosteroids and antihistamines

All remaining SAEs should be reported at investigator's earliest convenience. SAEs should be approved by the investigator (see Appendix 3 II). In addition, SAEs need to be reported in the (non-serious) AE section of the eCRF. The investigator will be requested to supply as much detailed information regarding the event as is available at the time of the initial contact.

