## 9.1. Time Period and Frequency of Collection and Reporting

The following timeframes for reporting apply from signature of the informed consent or, where informed consent is deferred, from the documented decision timepoint of the responsible investigator and/or physicians to enroll the patient, on:

- All AEs, including AESIs and SAEs until 30 days following the last IFX-1 administration must be reported
- All pregnancies until 30 days after the last dose of treatment with IFX-1 must be reported until completion of the pregnancy, as described in Section 9.5.2

Any time outside of the time period specified above, in addition, any study drug-related SAEs brought to the attention of an investigator must be reported immediately to the sponsor.

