#### **9.2.1.1. Follow-up Reporting of Serious Adverse Events**

Follow-up information on SAEs must be reported by the investigator within the same time frames as the initial reporting.

A follow-up report to an SAE should be prepared if any relevant change in the condition of the patient occurs after the initial report, or any new relevant information becomes available.

Further information on follow-up procedures is given in Appendix 3 II.

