#### **Follow-up of AEs, including AESIs and SAEs**

- The investigator is obligated to perform or arrange for the conduct of supplemental measurements and/or evaluations as medically indicated or as requested by the sponsor or the safety vendor to elucidate the nature and/or causality of the AE as fully as possible. This may include additional laboratory tests or investigations, histopathological examinations, or consultation with other health care professionals.
- In case of persisting SAEs, follow-up must continue until the AEs have resolved to grade  $\leq 1$  or baseline or are deemed irreversible by the investigator.
- If a patient dies during participation in the study or during a recognized follow-up period, the investigator will provide the safety vendor with a copy of any post-mortem findings including histopathology, if any would become available.
- The investigator will submit any updated SAE data to the safety vendor within 24 hours of receipt of the information.

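### A drug-related SAE outside the collection window must be reported immediately; inside it, the same SAE has no fixed deadline unless it is fatal or on the life-threatening list

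*Combined protocol and SAP*

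**What the plan says.** Section 9.1 of protocol Version 4.0 sets the window: "All AEs, including AESIs and SAEs until 30 days following the last IFX-1 administration must be reported". For any time outside it, "any study drug-related SAEs brought to the attention of an investigator must be reported immediately to the sponsor". That duty depends on relatedness alone and is not limited by severity.

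Section 9.2.1 sets the times for initial reports. Its opening line, "SAEs that should be reported within 24 hours on the SAE form are", introduces two groups: "Events with fatal outcome" and "New life-threatening events, defined as". The second group is followed by organ thresholds and named event types. For everything else, "All remaining SAEs should be reported at" the investigator's earliest convenience. No hours or days are given, and relatedness plays no part.

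For updates, Section 9.2.1.1 says "Follow-up information on SAEs must be reported by the investigator within the same time frames as the initial reporting", while Appendix 3 II says "The investigator will submit any updated SAE data to the safety vendor within 24 hours of receipt of the information". Appendix 3 II also applies a 24-hour limit to initial reports, but identifies the SAEs concerned only by pointing to Section 9.2.

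**The concern.** The ordering is the reverse of what one would expect. The window opens at consent, or at the enrolment decision where consent is deferred, and closes 30 days after the last dose. Every dose therefore falls inside it, and so does the period in which a reaction to study drug is most likely to be seen. Yet a related SAE has a strict rule outside the window and, if it is neither fatal nor listed, an open-ended one inside.

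What is at stake is how quickly the sponsor and the safety vendor learn of a related event while this patient and others are still being dosed. Four of the six planned doses are due by day 8 (days 1, 2, 4 and 8, Section 7.2.1.2). The vendor's submission of suspected unexpected serious adverse reactions (Section 9.8) cannot start until the site reports.

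**Working it through.** No figure in the plan bears on this and no formula applies, so the check sets the rules side by side.

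**Initial report of an SAE judged related to study drug**

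| Event | Outside the window | Inside the window |
|---|---|---|
| Fatal | Immediately (9.1) | 24 hours (9.2.1) |
| On the life-threatening list | Immediately (9.1) | 24 hours (9.2.1) |
| Any other related SAE, e.g. serious only because it prolongs hospitalization | Immediately (9.1) | Investigator's convenience, no limit (9.2.1) |

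The third row is the problem.

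**Does another section supply the missing limit?**

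1. *Appendix 3 II, SAE reporting.* Its 24-hour limit covers the SAEs that Section 9.2 outlines. Read narrowly, that is the same closed list and nothing is added. Read broadly, it is every SAE, which contradicts the last paragraph of Section 9.2.1. Either reading leaves something to reconcile.
2. *Section 9.6.* AESIs are sent to Appendix 3, which leads back to item 1.
3. *Section 8.2.* Sites are asked to raise safety concerns with the sponsor straight away, to decide whether the patient continues on study drug. This is a duty to talk and sets no time for an SAE report.
4. *Section 9.1.2.* Related SAEs after the end of study go through the regular system with no time stated, so the rule outside the window is not uniform either.

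**An example from the protocol's own thresholds.** Section 9.5.3 requires potential drug-induced liver injury to be handled as an SAE when ALT or AST exceeds 3 × ULN and total bilirubin exceeds 2 × ULN, with no cholestatic or other apparent cause. The liver line in Section 9.2.1 starts above 20 × ULN for AST or ALT, or above 10 × ULN for bilirubin. A qualifying case with transaminases no higher than 20 × ULN and bilirubin no higher than 10 × ULN is therefore an SAE by definition but does not reach the 24-hour liver line. Unless it is fatal or counts as life-threatening on other grounds, it has no fixed deadline.

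**Updates.** For an unlisted SAE, Section 9.2.1.1 carries over the open time frame of the initial report, while Appendix 3 II asks for 24 hours. Taken together, an update can have a firmer deadline than the first report of the same event.

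The corresponding sections of Version 2.0 have the same structure.

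**The case against.** The strongest case on the other side has several parts.

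- **Section 8.2 already protects the patient.** An SAE judged drug-related is plausibly a safety concern to be raised with the sponsor at once. This stands as mitigation: the sponsor may hear informally. It does not set a time for the report that the vendor's processing depends on.
- **The tiers are deliberate.** Section 9 and Appendix 3 III explain why ICU reporting is selective. This stands for unrelated complications. It does not explain why relatedness counts outside the window and not inside.
- **Some text is unavailable.** A block between the visible end of Section 9.2.1 and Section 9.2.1.1 is absent from the copy reviewed and cannot be checked. Whatever it holds, the open-ended rule remains in the visible text.
- **The effect is slight.** No endpoint, alpha or power is touched. The IDMC meets every 3 months (Section 5.5), so a lag of days would seldom change what it sees. Both points stand.

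A reader might also infer more than the documents support:

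- *That a hypersensitivity reaction could go unreported while its patient keeps being dosed.* Appendix 5, Table 6 already ends dosing after severe and life-threatening infusion reactions, and the life-threatening ones are on the 24-hour list. This example should not be used.
- *That Section 9.2.1.1 and Appendix 3 II cannot both be obeyed on updates.* A site that sends every update within 24 hours satisfies both. The wording is untidy but not impossible to follow.

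**Conclusion.** The inconsistency is real and can be seen in the protocol text alone. As written, a related SAE that is neither fatal nor on the life-threatening list has the weakest reporting rule during the period when patients are being dosed. Potential drug-induced liver injury below the listed thresholds is a concrete instance.

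The set affected is every related, non-fatal, unlisted SAE inside the window. Its number and any resulting delay cannot be estimated from the documents. The documents do not show that a signal would be missed: all SAEs in the window must be reported, and only their timing is open.

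Two assumptions are used. The window is taken as Sections 9.1 and 9.1.1 define it; the opening of Section 9 instead says collection runs to end of treatment, and this should be tidied at the same time. The Appendix 3 II reference to Section 9.2 is taken as pointing to the 24-hour list. On the broader reading the finding becomes a direct contradiction with Section 9.2.1, and the remedy is the same.

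**What to change.** Reconcile Sections 9.1 and 9.2.1 and Appendix 3 II:

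- In Section 9.2.1, add to the 24-hour group every SAE that the investigator considers related to study drug, counted from awareness. Appendix 3 II already requires a causality assessment before the first transmission, so the site has the information it needs to apply the rule.
- Keep the slower track for unrelated SAEs that are not on the list.
- In Appendix 3 II, name the groups the 24-hour limit covers instead of referring to Section 9.2 as a whole.
- In Section 9.2.1.1, state that updates follow the 24-hour rule in Appendix 3 II.

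The cost is wording plus somewhat more expedited forms. A fixed number of days for unrelated SAEs, or a 24-hour limit for every serious AESI whether related or not, would go beyond reconciling the text. Those are preferences and are not part of this recommendation.

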#### **9.2.1.1. Follow-up Reporting of Serious Adverse Events**

Follow-up information on SAEs must be reported by the investigator within the same time frames as the initial reporting.

A follow-up report to an SAE should be prepared if any relevant change in the condition of the patient occurs after the initial report, or any new relevant information becomes available.

Further information on follow-up procedures is given in Appendix 3 II.

#### **9.2.2. Determination of Relatedness**

The investigator will use medical consideration to determine the relatedness of an AE with the study drug based on the following definitions (see also Appendix 3 II):

##### **Unrelated**

This category applies to AEs that are due to extraneous causes (disease, concomitant medication, environment, etc.) and are not related to the administration of study drug.

##### **Unlikely Related**

This category applies to AEs that are unlikely related to the administration of the study drug. The relationship of an AE to the study drug can be considered unlikely related if (must have first two criteria listed below):

- The AE does not follow a reasonable temporal sequence from administration of the drug
- The AE could readily have been a result of the patient's clinical state or other underlying medical condition, environmental or toxic factors, or other modes of therapy administered to the patient
- The AE does not follow a known response pattern to the suspected drug
- The AE does not reappear or worsen when the study drug is re-administered

### **Possibly Related**

This category applies to AEs that are unlikely to be related to the administration of the study drug, but the possibility cannot be ruled-out with certainty. The relationship of an AE to the study drug can be considered possibly related if (must have first two criteria listed below):

- The AE follows a reasonable temporal sequence from administration of the study drug
- The AE could readily have been a result of the patient's clinical state, environmental or toxic factors, or other modes of therapy administered to the patient
- The AE follows a known response pattern to the suspected study drug

### **Probably Related**

This category applies to AEs that are considered with a high degree of certainty to be related to the administration of the study drug. The relationship of an AE to the study drug can be considered probably related if (must have first three criteria listed below):

- The AE follows a reasonable temporal sequence from administration of the study drug
- The AE could not be reasonably explained by the known characteristics of the patient's clinical state, environmental or toxic factors, or other modes of therapy administered to the patient
- The AE disappears or decreases upon cessation of study drug or reduction in dose
- The AE follows a known response pattern to the suspected study drug

### **Definitely Related**

This category applies to AEs that are determined with certainty to be related to the administration of the study drug. The relationship of an AE to the study drug can be considered definitely related if (must have first three criteria listed below):

- The AE follows a reasonable temporal sequence from administration of the study drug or study drug levels have been established in body fluids or tissues
- The AE could not be reasonably explained by the known characteristics of the patient's clinical state, environmental or toxic factors, or other modes of therapy administered to the patient
- The AE disappears or decreases upon cessation of study drug or reduction in dose and, if applicable, appears upon re-challenge
- The AE follows a known response pattern to the suspected study drug
- There are exceptions when an AE does not disappear upon discontinuation of the study drug, yet study drug relatedness clearly exists; e.g., 1) tardive dyskinesia, 2) fixed drug eruptions

### 9.3. Death Reporting

The site should follow all patients for survival and collect information around the death on the appropriate eCRF form until the end of the study.

Primary cause of death should be reported in AE section and SAE form, as well as appropriate eCRF section(s). If symptoms of disease progression occurred and constitute the primary cause of death, these symptoms could be reported as fatal (S)AE (see Section 9.2.2).

### 9.4. Abnormal Laboratory Values/Vital Signs/ECG/Physical Examination

Abnormalities of laboratory results / vital signs / ECG / physical examination should be reported as AEs, particularly if at least one of the following is met:

- Any criterion for an SAE is fulfilled
- The abnormality causes the patient to discontinue from the study treatment
- The abnormality causes the patient to interrupt the study treatment or a modification of dosing
- The abnormality requires intervention as corrective treatment or consultation
- The investigator judges that the abnormality is clinically significant and should be reported as an (S)AE in the eCRF

All laboratory tests for which clinically significant abnormal results are observed after the initiation of study treatment should be repeated until the values return to normal or to a stable status. Clinically significant abnormal laboratory results must be reported as an AE. The frequency with which such checks should be made will be made by investigator's discretion depending on the degree of abnormality. The reporting of laboratory/vital signs/ECG/physical examination abnormalities as both AEs and a specific finding of laboratory values/vital signs/ECG should be avoided.

Abnormal laboratory value testing will follow special considerations for conditions in the ICU (refer also to Appendix 3, III Special Considerations for Assessment of Adverse Events in an ICU Setting). It must be noted that clinically significant laboratory deterioration as assessed by the investigator must be documented in the respective eCRF section. However, it is preferred to document the condition or disease underlying the aberrant laboratory value (e.g., renal failure rather than hyperkalemia) rather than the laboratory value only.

### 9.5. Events to be Handled as SAEs

#### 9.5.1. Overdose Reporting

An overdose is defined as the accidental or intentional ingestion or infusion of any dose of a product that is considered both excessive and medically relevant.

All symptoms associated with the overdose should be handled as SAEs.

Refer to Section 7.6 for details on the treatment of overdose.

### **9.5.2.      Pregnancy Reporting**

If the patient or partner of a patient participating in the study becomes pregnant during treatment or within 30 days after the last dose of treatment with IFX-1, the investigator should report the pregnancy to [QLS\\[contact]](mailto:[contact]) via e-mail within 24 hours of being notified. The safety vendor will then forward the pregnancy reporting form to the investigator for completion. In case that e-mail contact is not possible, the site can provide an initial pregnancy report in the SAE section of the SAE form and transmit this via the SAE FAX line: [contact].

A patient becoming pregnant while on IMP will immediately be discontinued from treatment and the EOT visit will be performed.

The patient or partner should be followed by the investigator until completion of the pregnancy. If the pregnancy ends for any reason before the anticipated date, the investigator should notify the sponsor. At the completion of the pregnancy, the investigator will document the outcome of the pregnancy. If the outcome of the pregnancy meets criteria for immediate classification as an SAE (i.e., postpartum complication, spontaneous abortion, stillbirth, neonatal death, or congenital anomaly), the investigator should follow the procedures for reporting as SAE.

### **9.5.3.      Drug-induced Liver Injury**

Potential drug-induced liver injury is considered an important medical event. Although it is not always serious by regulatory definition, such event must be handled as SAE.

Wherever possible, timely confirmation within 48 to 72 hours of initial liver-related laboratory abnormalities should occur prior to the reporting of a potential drug-induced liver injury event. All occurrences of potential drug-induced liver injuries, meeting the defined criteria, must be reported as SAEs.

Potential drug-induced liver injury is defined as:

- ALT or AST elevation  $> 3 \times \text{ULN}$

AND

- Total bilirubin  $> 2 \times \text{ULN}$ , without initial findings of cholestasis (elevated serum alkaline phosphatase)

AND

- No cholestatic or other immediately apparent causes of AST or ALT elevation and hyperbilirubinemia, including, but not limited to, viral hepatitis, pre-existing chronic or acute liver disease, or the administration of other drug(s) known to be hepatotoxic

#### **9.5.4. Suspected Transmission of an Infectious Agent (Pathogenic or Non-pathogenic) via Study Drug**

For the purposes of reporting, any suspected transmission of an infectious agent via the investigational drug should be considered as an SAE.

A transmission of an infectious agent may be suspected from clinical signs or symptoms, or laboratory findings indicating an infection in a patient exposed to a medicinal product.

In the context of evaluating a suspected transmission of an infectious agent via a medicinal product, care should be taken to discriminate, whenever possible, between the cause (e.g., injection/administration) and the source (e.g., contamination) of the infection and the clinical conditions of the patient at the time of the infection (immuno-suppressed /vaccine).

#### **9.6. Adverse Events of Special Interest**

AESIs are events that are considered to have a special meaning or importance for a particular drug or class of drugs. They may be non-serious or serious. Therefore, they should be closely monitored. The site must report all AESIs that occur during the study period, whether considered to be related to IP or not, according to Appendix 3. Moreover, AESIs should be documented in the general AE section of the eCRF as well as in the patient file.

This is the first study investigating IFX-1 in COVID-related pneumonia. Clinical experience with IFX-1 has been generated in more than 300 patients with inflammatory diseases, including sepsis and HS.

For this study, the following AEs are defined as AESIs:

- Infusion reactions, including hypersensitivity or anaphylaxis during or after IFX-1 infusion:

All patients should be observed closely during the IFX-1 administration and for ≥ 60 minutes thereafter. The intravenous line should remain open during the observation to allow for administration of intravenous drugs, if necessary. Medication for infusion reactions should be available for immediate use. Medical staff has to be trained in resuscitation and immediate intensive care has to be easily accessible in case of severe life-threatening events. Mild to moderate reactions may be treated by slowing or interruption of the infusion, or with supportive treatment (Appendix 5).

For any potential infusion event, the investigator should closely monitor for a potentially developing or existing anaphylactic reaction. In case an anaphylactic reaction is anticipated, appropriate immediate actions should be taken according to the severity or stage of the detected anaphylactic reaction.

- Meningitis and meningococcal sepsis:

In case of signs of meningitis at any time during the study, the IMP should be discontinued if meningitis is confirmed. The patient must be closely monitored and the guidelines for treatment of meningitis should be followed ([Tunkel et al. 2004](#), [van de Beek et al. 2016](#)). This includes lumbar puncture, blood culture testing, immediate start of treatment with dexamethasone and intravenous antibiotics (combination therapy with ampicillin and third generation cephalosporin), and a search for the focus of the infection (e.g., CT or MRI).

- Infections other than COVID-19 (SARS-CoV-2) infections

In patients with bacterial infection, depending on the severity of the infections, it is important that concomitant antibiotic therapy is administered during treatment with IFX-1 to ensure appropriate control of the source of the infection. The investigator should pay close attention to the choice of an appropriate broad-spectrum antibiotic treatment according to applicable guidelines.

Note: A severe infection can be suspected whenever an IV antibiotic, antifungal, or antiviral intervention would be indicated under non-ICU conditions or an invasive intervention would have been indicated.

